Crude as well as adjusted hazard ratios will be calculated. The appropriate confounding variables will be built into the statistical model. Based on the expectation of a small absolute number of serious outcomes of interest the number of confounding variables will be limited to established risk factors for these outcomes. For anemia these will include age, duration of current use, and family history of bleeding disorders and a past history of anemia. For depression, age, chronic pelvic pain, anxiety disorder and a family history of depression are proposed. For 'treatment failure' chronic pelvic pain, age and previous surgical treatment will be included. The final decision on and the addition of other confounding variables (e.g. country) will be made by the Safety Monitoring and Advisory Council before the first interim analysis of follow-up data. In addition, alternative analysis will be performed with other potential baseline risks to check the appropriateness of this decision.

A detailed statistical analysis plan will be developed by the Principal Investigator during the first year after study start. The final analysis plan will be approved by the Safety Monitoring and Advisory Council before the first interim analysis of follow-up data.

Biannual interim reports will be provided to the funder following release of the interim analyses results by the independent Safety Monitoring and Advisory Council (cf. section 13).

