#### 5.4.2 Regression models

Regression analysis will be performed if a sufficient number of confirmed events are available for estimation, i.e. n≥5 confirmed events in each of the comparison groups.

Potential confounders such as

- age, personal and family history of depression, history of anemia, history of bleeding disorders and severity of pain will be included as time-invariant cofactors.
- EMT user type at follow up, use of Antidepressants/SSRI and current or worsening depression (primary outcome) will be included as time-dependent cofactors.

For each primary outcome, a summary table with predefined potential prognostic factors and the corresponding relative risk estimators is provided.

The final decision on the confounding variables will be made by the Safety Monitoring and Advisory Council:

Primary outcome variable	Predefined Prognostic Factors 	
Anemia	Age, history of anemia, history of bleeding disorders	
Depression	Age, family and personal history of depression, use of Antidepressants/SSRI	
Treatment Failure	Age, family and personal history of depression, severity of pain	

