## 10. Appendix

### I Baseline questionnaire

#### **INAS-VIPOS**

International Active Surveillance Study of Medication Used for the Treatment of Endometriosis:  $\underline{V} is anne \ \underline{P} ost-approval \ \underline{O} bservational \ \underline{S} tudy$ 

	- Baseline Questionnaire -
	Country Physician no. Patient no. ID
If you	have any questions, please call our toll-free number: [telephone number].
	To be filled in by the physician!
1.	What is the name of the medication for endometriosis that you prescribed to your patient today?,
1a.	If you prescribed an oral contraceptive today, have you prescribed an extended regimen? 2
	□ No □ Yes
2.	Please tick the appropriate box to describe today's prescription: 3
	☐ First-time hormonal prescription/no previous hormonal treatment
	☐ Repeat of the same hormonal treatment after a medication break of at least 4 weeks
	☐ Switching from another hormonal treatment without a relevant break (< 4 weeks)
	☐ Switching from another hormonal treatment after a break of at least 4 weeks
3.	How would you classify your patient's endometriosis? 4
	□ Diagnosis based only on clinical symptoms
	☐ Endometriosis confirmed via surgery / laparoscopy
4.	In the last 2 years, how many surgical procedures (diagnostic and/or therapeutical) has your patient received for the management of her endometriosis?
	Number of surgical procedures:
	To be filled in by the study participant!
Pers	onal Data
5.	Please give your date of birth: $\bigcup_{\text{day}}^{\square} \bigcup_{0}^{\square} \bigcup_{\text{month}}^{\square} \bigcup_{\text{year}}^{\square} \bigcup_{\text{year}}^{\square} \bigcup_{0}^{\square} \bigcup_{0}^{\square} \bigcup_{\text{year}}^{\square} \bigcup_{0}^{\square} \bigcup_{0}^{$
6.	What is your height?, cm
7.	What is your weight?kg
Gyn	ecological History
8.	How old were you when you had your first menstrual bleeding?
9.	Have you ever been pregnant? 12
	□ No → go to question 10 □ Yes
9a.	If yes , when did you last give birth? $\frac{DDD}{D}_{12} = \frac{DDD}{D}_{13} = \frac{DDDD}{D}_{14} = DDDDDDDDDDDDDDDDDDDDDDDDDDDDDDDDDDD$
9b.	How many live births have you had?
9c.	How many abortions/miscarriages/still births have you had?
End	ometriosis
10a.	When did you first experience endometriosis symptoms?
10b.	When were you first diagnosed with endometriosis by a physician?    M   M   20   Y   Y   Y   Y   Y   Y   Y   Y   Y

f I

Supporting document SOP BMT 01.09 – Doc 5002.02 – Effective date 21.03.2017

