## III List of potential prognostic factors for primary outcomes

Primary Outcome	Predefined Potential Prognostic Factors
Anemia	EMT user type at follow-up, age, history of anemia, history of bleeding disorders
Depression	EMT user type at follow-up, age, family and personal history of depression, use of Antidepressants/SSRI, severity of pain
Treatment Failure	EMT user type at follow-up, age, family and personal history of depression, current/worsening depression, severity of pain

Supporting document SOP BMT 01.09 – Doc 5002.02 – Effective date 21.03.2017

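### Protocol section 11 puts previous surgical treatment in the treatment-failure model; the SAP leaves it out without a recorded decision, so the superiority comparison is open to residual confounding of unknown size and direction

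*Protocol*

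**What the plan says.** Protocol section 11 names the covariates for each primary outcome. For the superiority outcome it says: "For 'treatment failure' chronic pelvic pain, age and previous surgical treatment will be included". The depression covariates in the same paragraph are only put forward as a proposal, so the surgery wording is the firmer of the two. The list is not closed, however: "The final decision on and the addition of other confounding variables (e.g. country) will be made by the Safety Monitoring and Advisory Council", to be settled before the first interim analysis of follow-up data. A further safeguard follows: "In addition, alternative analysis will be performed with other potential baseline risks to check the appropriateness of this decision".

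SAP section 5.4.2 gives the treatment-failure factors as "Age, family and personal history of depression, severity of pain". Its general list of fixed covariates reads "age, personal and family history of depression, history of anemia, history of bleeding disorders and severity of pain will be included as time-invariant cofactors". Appendix III, the widest list, has "EMT user type at follow-up, age, family and personal history of depression, current/worsening depression, severity of pain". None of these contains surgery. On authority the SAP says only: "The final decision on the confounding variables will be made by the Safety Monitoring and Advisory Council".

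The data exist. Item 4 of the baseline questionnaire (SAP Appendix I) asks the physician: "In the last 2 years, how many surgical procedures (diagnostic and/or therapeutical) has your patient received for the management of her endometriosis". Item 14 asks the patient to list her endometriosis operations with dates. The planned mock tables show both, descriptively, in sections B-4.4 and B-4.5.

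**The concern.** Treatment failure is the only one of the three primary hypotheses framed as superiority (SAP 5.2, null hypothesis OR ≥ 1), and allocation follows routine prescribing. A non-inferiority bound of HR 2 leaves some room for modest confounding. A null value of 1 leaves none, because any imbalance in a factor related to failure moves the estimate across it or away from it. If surgical history differs between DNG and OAED users and also predicts stopping for inefficacy or side effects, part of the observed difference reflects who received which drug.

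The Protocol named this factor, the study collected it, and the SAP does not use it in the comparison. A reader of the final report could not tell whether that was a considered choice.

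**Working it through.** **1. Covariates side by side.**

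| Protocol section 11 | Counterpart in SAP 5.4.2 / Appendix III |
|---|---|
| Age | Age |
| Chronic pelvic pain | Severity of pain |
| Previous surgical treatment | None |

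Surgery is the only Protocol covariate for this outcome with no SAP counterpart. SAP 5.4.2.1 sends the 5.4.2 factors into the adjusted Cox models, so the omission carries through to the adjusted hazard ratio in Section D-3.

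**2. Whether something else stands in for it.**
- Pain severity: the Protocol's introduction says pain tracks poorly with how extensive the disease is, so on the plan's own account it is not a substitute.
- EMT user type (starter, switcher, restarter) reflects drug history, not surgery.
- Stratification by surgically confirmed diagnosis: SAP section 8 lists it for the Section C incidence tables. The Section D comparisons are listed without it. A surgical diagnosis is also not the same as surgical treatment.
- The Protocol's alternative analyses with other baseline risks are not carried into the SAP.

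**3. The plan's own figure, for scale.** No stated figure is in dispute. Table 4 uses 25% versus 30%, 2,950 DNG and 1,475 reference women-years, and one-sided alpha 0.0167 (z = 2.127). I treat women-years as counts, with power = Φ[(Δ − z·s0)/s1], where
- s0 = √[p̄(1 − p̄)(1/2,950 + 1/1,475)]
- s1 = √[p_D(1 − p_D)/2,950 + p_O(1 − p_O)/1,475]

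This gives Φ[(0.05 − 2.127 × 0.01410)/0.01435] = 91.8%, against the stated 90%. The planned OR is (0.25/0.75)/(0.30/0.70) = 0.78.

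**4. Illustration on assumed values.** The documents give neither the surgery–failure association nor the prevalence of surgery by cohort. Assume failure of 35% with prior surgery and 25% without, and no drug effect. The crude risk is then prevalence × 0.35 + (1 − prevalence) × 0.25.

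| Prior surgery, DNG vs OAED | Failure, DNG | Failure, OAED | Crude OR |
|---|---|---|---|
| 40% vs 50% | 0.4×0.35 + 0.6×0.25 = 29% | 0.5×0.35 + 0.5×0.25 = 30% | 0.95 |
| 30% vs 60% | 0.3×0.35 + 0.7×0.25 = 28% | 0.6×0.35 + 0.4×0.25 = 31% | 0.87 |
| 60% vs 30% | 31% | 28% | 1.16 |

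With the step 3 formula, the chance of wrongly declaring DNG superior is:
- row 1: Φ[(0.01 − 2.127 × 0.01452)/0.01457] = 7.6%
- row 2: Φ[(0.03 − 2.127 × 0.01447)/0.01461] = 48%

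The nominal level is 1.67%. In row 3 the bias runs against DNG.

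**5. Sensitivity to the assumed association.** Fix OAED failure at 30% and compare surgery in 40% of DNG with 50% of OAED women. Failure risk ratios for surgery of 1.25, 1.5 and 2.0 then give crude ORs of 0.97, 0.94 and 0.91. With 30% versus 50%, the ORs are 0.94, 0.89 and 0.82. These are crude figures; adjustment for pain and the other SAP factors could remove part of the distortion.

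**The case against.** The strongest reply is that the Protocol list was provisional. The sentence after the quoted one gives the Council the final say, and the Council also approves the SAP. The SAP cites a protocol amendment of September 30, 2017 whose text is not among the documents reviewed, and Council decisions are not supplied either. A reader might infer that the SAP breaches the Protocol. The documents do not support that: an authorised change is possible. What stands is that the SAP records no such change and still describes the Council's decision as pending. This is in a version written after recruitment ended in June 2016, whereas the Protocol wanted the decision before the first interim analysis of follow-up data.

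A reader might also infer that disease severity goes unadjusted. It does not: pain severity is in the model, and failure is displayed by surgically confirmed diagnosis. Those displays would help reveal an imbalance but do not adjust the Section D estimate.

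Finally, a reader might infer a bias in DNG's favour of about 3 of the 5 planned points. That comes from one chosen scenario. Nothing in the documents says that women with prior surgery fail more often or are steered to a particular drug, and effective excision could lower later failure. This objection stands in full as regards size and direction.

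**Conclusion.** The point holds as an unexplained gap between Protocol and SAP on the one superiority test. A covariate that the Protocol said would enter the model is absent from every SAP list. No recorded decision or reason accounts for it, and no other model term replaces it. The consequence is exposure to residual confounding by surgical history, not a demonstrated bias. On the assumed risks in the working, with no drug effect, the crude distortion ranges from 1 point in DNG's favour, through 3 points in its favour, to 3 points against it, beside a planned difference of 5. Those figures rest on assumed prevalences and risks and on treating women-years as counts. No stated sample size, power or alpha changes.

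**What to change.** Add previous therapeutic endometriosis surgery (yes/no) to the treatment-failure row of SAP 5.4.2 and Appendix III. Derive it from patient item 14, which records the operation and its date. The physician's item 4 does not match the Protocol term, because it counts diagnostic procedures too and covers only the last two years. Keep it as a supporting or sensitivity variable.

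Use the covariate in whichever adjusted model tests superiority. SAP 5.2 states the hypothesis as an odds ratio, while Section D-3 reports a Cox hazard ratio, so editing the 5.4.2 table alone would not adjust an odds ratio.

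If the Council deliberately dropped surgery, cite the decision and its reason, and report a sensitivity model that includes it.

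The cost is one entry in two tables and one derived variable. Mock Table B-4.5.1 already separates diagnostic from therapeutic procedures, so no new data are needed. The Protocol limits covariates because it expects few serious outcomes. That reason does not apply here: at Table 4's figures, 2,950 × 0.25 + 1,475 × 0.30 = 1,180 failures.

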12. SIZE OF THE STUDY AND EVALUTION

The 3 to 6 year follow-up of 25,000 women should result in approximately 89,000 documented women-years. This estimate is based on the assumptions that (1) ZEG's physicians' network could recruit 25,000 women within three years, and (2) the annual drop-out rate is 10% (based on the EURAS-OC [1] and LASS studies). Details are provided in Table 1 and are based on the assumption that the follow-up period is a maximum of 6 years.

	Sub-cohorts recruited during the					
1 st study year		2 nd study year		3 rd study year		
Time (y)*	No. of women	Time of observation	No. of women	Time of observation	No. of women	Time of observation
1	7,910	4,035				
2	7,119	7,515	7,910	4,035		
3	6,407	6,763	7,119	7,515	7,910	4,035
4	5,766	6,087	6,407	6,763	7,119	7,515
5	5,190	5,478	5,766	6,087	6,407	6,763
6	4,671	4,930	5,190	5,478	5,766	6,087
WY (total)		34,808		29,878		24,400
WY (grand total)	89,086					

Table 1: Expected observation time (max. 6 years follow-up): Patient recruitment within 3 years (annual recruitment rate = 8,334 women)

* Time after start of recruitment

** The number of recruited women equals 8,334. However, the number of women at the end of the first year is lower because some women will drop out during the first year (daily drop-out rate is ~ 0.029%).

The study was designed to analyze rare events (according to the CIOMS classification 1 - 10 and less than 1 event(s) per 10,000 women-years, respectively). The adverse events of particular interest for the sample size calculations are anemia, clinically relevant depression and treatment failure.

The background prevalence of anemia in premenopausal European women is approximately 10-15% [14]. Based on this high prevalence and the fluctuating character of the disease the investigators anticipate an incidence of new or recurrent anemia in an active surveillance study of 0.01-0.02. The sample size calculation is based on a conservative estimate of 0.01 (or 1 event per 100 WY).

A conservative estimate of the prevalence rate for depression in women with endometriosis is 20%. This figure is based on a systematic literature review of the available evidence and an analysis of EURAS/INAS results [10-12]. For newly diagnosed or worsening depression the expected incidence rate is at least 0.01. Based on this incidence, the sample size outlined below was calculated; in case the study shows other incidence rates at a later point in time, a re-calculation may be necessary and will be discussed with the Safety Monitoring and Advisory Council if required.

Based on the natural history of endometriosis treatment, we anticipate that the majority of women will stop or change treatment regimes during the course of this study. We expect an incidence rate of women ceasing or changing treatment ('treatment failure') for other endometriosis medications due to lack of efficacy, loss of efficacy or an adverse drug reaction of at least 0.3. For the DNG cohort a proportion of 0.25 of the total study population seems to be realistic.

Overall, 3 hypotheses will be tested (cf. section 11). The problem of multiple comparisons is addressed by using Bonferroni-Holm correction to maintain the overall error rate by testing each individual hypothesis at a statistical significance level of 1/3 times what it would be if only one hypothesis were tested (i.e., the individual tests will be based on an α level of 0.0167 instead of 0.05).

Power calculations based on the incidences given above showed that approximately 84,000 women-years would be needed to show non-inferiority of DNG versus other endometriosis medications for anemia. The calculations for anemia are based on the assumptions given in Table 2. In essence, the study is powered to exclude a two-fold risk of anemia for the DNG with at least 10% of the total exposure – if the true risk of anemia is not different for the relevant sub-cohorts.

Table 2: Power calculation^[15] for anemia based on the assumption that the true incidence of DNG cohort is not different from other endometriosis medications (reference cohort)

Test significance level, α (one-sided)	0.0083 (= 0.0167 two-sided)
Anemia Incidence for reference cohort	0.01
Non-inferiority margin	0.01 (equal to the anemia incidence for the reference cohort)
Expected anemia incidence for DNG cohort	0.01
Power (%)	90
Proportion of DNG users (% of study population)	10
Proportion of reference users (% of study population)	5
Required women years in DNG cohort	8,400
Required women years in reference cohort	4,200
Total women years	84,000

Furthermore, 84,000 WY would be sufficient to also exclude a two-fold risk of clinically relevant depression (cf. Table 3), assuming that DNG accounts for at least 10% of the total exposure.

For 'treatment failure' approximately 29,500WY will be required to show that DNG is superior to other endometriosis medications (cf. Table 4), assuming that the proportion of DNG, danazol and GnRH agonists users each account for 10% of the total exposure.

Table 3: Power calculation^[15] for depression based on the assumption that the true incidence in the DNG cohort is not different from the reference cohort

Test significance level, α (one-sided)	0.0083 (= 0.0167 two-sided)
Depression Incidence for reference cohort	0.01
Non-inferiority margin	0.01 (equal to the depression incidence for the reference cohort)
Expected depression incidence for DNG cohort	0.01
Power (%)	90
Proportion of DNG users (% of study population)	10
Proportion of reference users (% of study population)	5
Required women years in DNG cohort	8,400
Required women years in reference cohort	4,200
Total women years	84,000

Table 4: Power calculation^[15] for 'treatment failure' based on the assumption that the trueincidence in the DNG cohort is $\sim 2,500/10,000$ compared to $\sim 3,000/10,000$ in theother endometriosis medications cohort.

Test significance level, α (one-sided)	0.0167	
Incidence of treatment failure for other endometriosis medications cohort	0.30	
Clinically relevant difference	0.05	
Expected incidence of treatment failure for DNG cohort	0.25	
Power (%)	90	
Proportion of DNG users (% of study population)	10	
Proportion of reference users (% of study population)	5	
Required women years in DNG cohort	2,950	
Required women years in other endometriosis medications cohort	1,475	
Total women years	29,500	

These power calculations suggest that this study is sufficiently powered to show noninferiority of DNG compared to established endometriosis treatments with regard to anemia and clinically relevant depression, as well as superiority with regards to 'treatment failure'. However, exact power calculations based on actual incidences and drop-out rates should be done on the basis of two years follow-up data. If these calculations do not confirm the assumed incidences and drop-out rates, the independent Safety Monitoring and Advisory Council (SMAC) may discuss the need for adapting patient numbers and follow-up times.

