11. DATA ANALYSES

Three primary outcomes of interest, anemia, depression and treatment failure⁷, will be analyzed for inferential statistics.

Based on available data and pharmacological/pharmacokinetic considerations the *a priori* assumption is that use of DNG is not associated with an increased risk of

⁷ 'Treatment failure' is defined as cessation of treatment caused by lack of efficacy, loss of efficacy or an adverse drug reaction and does not include women who stop treatment after pre-defined treatment periods (eg. after six months for GnRH agonists).

anemia compared to approved hormonal medications used in the treatment of endometriosis ("endometriosis medications"). It is probable that statistical comparisons of DNG vs. other endometriosis medications will not show a difference. Therefore, a non-inferiority design to investigate the anemia risk of DNG had been chosen. The analysis will be based on the comparison of the upper confidence limit for the point estimate of the anemia hazard ratio with the predefined non-inferiority margin (cf. section 12).

The null hypothesis to be tested is: $HR_{anemia} \ge 2$ (i.e., the anemia hazard ratio for DNG vs. other endometriosis medications is higher or equal to 2). The alternative hypotheses are: $HR_{anemia} < 2$.

For clinically relevant depression (first episode or worsening), the *a priori* assumption is that no approved treatment for endometriosis is associated with a higher risk of depression compared with untreated endometriosis. A non-inferiority design has been chosen, with primary analysis based on the comparison of the upper confidence limit for the point estimate of the depression hazard ratio with the predefined non-inferiority limit (cf. section 12).

The null hypothesis to be tested is: $HR_{depression} \ge 2$ (i.e., the depression hazard ratio for DNG vs. other endometriosis medications is higher or equal to 2). The alternative hypothesis is: $HR_{depression} < 2$.

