 ${\bf 9}$  According Study Protocol, Amendment of September 30, 2017

Supporting document SOP BMT 01.09 – Doc 5002.02 – Effective date 21.03.2017

shows other incidence rates at a later point in time, a re-calculation may be necessary and will be discussed with the Safety Monitoring and Advisory Council if required.

Based on the natural history of endometriosis treatment, we anticipate that the majority of women will stop or change treatment regimen during the course of this study. We expect an incidence rate of women ceasing or changing treatment ('treatment failure') for other endometriosis medications due to lack of efficacy, loss of efficacy or an adverse drug reaction of at least 0.3. For the DNG cohort, a proportion of 0.25 of the total study population seems to be realistic.

Overall, 3 hypotheses will be tested (cf. section 11). The problem of multiple comparisons is addressed by using Bonferroni-Holm correction to maintain the overall error rate by testing each individual hypothesis at a statistical significance level of 1/3 times what it would be if only one hypothesis were tested (i.e., the individual tests will be based on an  $\alpha$  level of 0.0167 instead of 0.05).

Power calculations based on the incidences given above showed that approximately 84,000 womenyears would be needed to show non-inferiority of DNG versus other endometriosis medications for anemia. The calculations for anemia are based on the assumptions given in Table 2. In essence, the study is powered to exclude a two-fold risk of anemia for the DNG with at least 10% of the total exposure – if the true risk of anemia is not different for the relevant sub-cohorts.

**Table 2:** Power calculation [6] for anemia based on the assumption that the true incidence of DNG cohort is not different from other endometriosis medications (reference cohort)

Test significance level, α (one-sided)	0.0083 (= 0.0167 two-sided)
Anemia Incidence for reference cohort	0.01
Non-inferiority margin	0.01 (equal to the anemia incidence for the reference cohort)
Expected anemia incidence for DNG cohort	0.01
Power (%)	90
Proportion of DNG users (% of study population)	10
Proportion of reference users (% of study population)	5
Required women-years in DNG cohort	8,400
Required women-years in reference cohort	4,200
Total women years	84,000

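### The plan names Bonferroni-Holm but describes plain Bonferroni, costing about 5 points of power each for anemia and depression, and the SAP's 95% limits apply neither rule

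*Protocol*

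**What the plan says.** Protocol section 12 counts the primary tests ("Overall, 3 hypotheses will be tested (cf. section 11") and addresses multiplicity by "using Bonferroni-Holm correction to maintain the overall error rate by testing each individual hypothesis at a statistical significance level of 1/3 times" the single-hypothesis level. It then spells out the consequence: "the individual tests will be based on an α level of 0.0167 instead of 0.05". SAP section 4 repeats the sentence ("using Bonferroni-Holm correction to maintain the" and so on) and keeps the pointer to a section 11 that the SAP does not have; its hypotheses are in 5.2.

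In both documents, Tables 2 and 3 (anemia, depression) give the one-sided level as "0.0083 (= 0.0167 two-sided"). Table 4 (treatment failure) reads "Test significance level, α (one-sided) 0.0167".

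Non-inferiority for anemia and depression is decided by comparing an upper confidence limit with a hazard ratio of 2 (protocol section 11, SAP 5.2), but neither place gives the confidence level. SAP 5.4.2.1 provides 95% Wald limits for the Cox models, and the Section D table templates show 95% intervals. No ordering of p-values and no second or third testing level appears in either document.

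**The concern.** The name and the description are different procedures. In Holm's method only the smallest p-value faces alpha/3; if it succeeds, the next faces alpha/2 and the last faces alpha. The text holds every test at alpha/3.

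The verdicts can differ. Suppose the anemia test gives one-sided p = 0.010 and the other two are below 0.0083. Holm declares anemia non-inferior; the described rule does not. The 95% limits in the SAP add a third possible reading. These are the three primary hypotheses of a post-authorization safety study, so the decision rule should be unambiguous before the final data are analysed. At the same familywise error rate, the fixed rule also has less power than the procedure the plan names.

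**Working it through.** **Inputs.** Three hypotheses; alpha 0.05 two-sided, so alpha/3 = 0.0167 two-sided or 0.00833 one-sided; power 90%; margin HR 2 with true HR 1; DNG to reference exposure 2:1 (10% against 5%); 8,400, 4,200 and 84,000 women-years (WY) from Tables 2 and 3; treatment failure 0.25 against 0.30 from Table 4. For the event rate, "The sample size calculation is based on a conservative estimate of 0.01 (or 1 event per 100 WY"). The documents give no correlation between the test statistics, so 0 to 0.8 is assumed.

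**1. Reproduce the plan's figure.** Events = (z_α + z_β)² / [p(1−p)(ln HR)²] = (2.395 + 1.282)² / [(2/3)(1/3)(0.693)²] = 126.6, so 127. Then 127/0.01 = 12,700 WY, or 8,467 DNG and 4,233 reference, within 1% of 8,400 and 4,200. With DNG at 10% of exposure, 8,400/0.10 = 84,000. Anemia and depression are therefore sized for 90% power at one-sided alpha/3.

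**2. Set the rules side by side (one-sided).**

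| Ordered p-value | As described | Holm |
|---|---|---|
| smallest | 0.00833 | 0.00833 |
| middle | 0.00833 | 0.0125 |
| largest | 0.00833 | 0.025 |

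**3. Treatment failure at 84,000 WY.** Table 4 needs only 29,500 WY. With 8,400 and 4,200 WY treated as denominators of proportions, the pooled proportion is 0.2667 and the standard errors are 0.00836 (null) and 0.00850 (alternative). Power at 0.00833 = Φ[(0.05 − 2.394 × 0.00836)/0.00850] = Φ(3.53) = 0.9998. On an event basis: 8,400 × 0.25 + 4,200 × 0.30 = 3,360 events; mean statistic √(3,360 × 2/9) × ln(0.30/0.25) = 4.98; power Φ(4.98 − 2.39) = 0.995. Both exceed 99%.

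**4. Power under each rule.** I simulated three normal statistics, 2,000,000 draws. The means were 3.676 (= 2.394 + 1.282) for anemia and depression, and 5.92 (= 3.53 + 2.394, rounded) or 4.98 for treatment failure.

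| Assumed correlation | Anemia, depression (each): fixed → Holm | All three: fixed → Holm | All-three gain (points) |
|---|---|---|---|
| 0 | 0.90 → 0.954 to 0.955 | 0.806 to 0.809 → 0.913 to 0.915 | 10.5 to 10.8 |
| 0.3 | 0.90 → 0.951 to 0.952 | 0.819 to 0.822 → 0.916 to 0.917 | 9.6 to 9.7 |
| 0.5 | 0.90 → 0.949 | 0.831 to 0.832 → 0.920 to 0.921 | 8.8 to 8.9 |
| 0.8 | 0.90 → 0.944 | 0.856 → 0.929 | 7.3 |

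Treatment failure gains at most 0.3 points.

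**5. What the SAP output would do.** Comparing a 95% upper limit with HR 2 is a one-sided 0.025 test. Its power for anemia is Φ(3.676 − 1.960) = 0.957, above both rules, but three such tests bound the one-sided familywise error only at 3 × 0.025 = 0.075.

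**6. Sidedness.** As labelled, the one-sided levels in Tables 2 to 4 sum to 0.0083 + 0.0083 + 0.0167 = 0.0333, not 0.025.

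**The case against.** The text sits in the sample-size sections. Sizing at alpha/3, Holm's first step, is legitimate and conservative, and fixed alpha/3 controls familywise error, so the described rule produces no invalid claim. Bonferroni also gives simple simultaneous confidence limits, which suits decisions made on limits. All of this stands. It does not remove the contradiction, because the sentence says how the individual tests will be carried out, not only how the study was sized.

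A second objection concerns size. A reader might infer a loss of 5 points on every test and 14 points for all three. Those figures do arise (0.900 to 0.952 per test, 0.729 to 0.873 jointly), but only if all three tests have exactly 90% power and are independent. The plan's own figures put treatment failure above 99% at 84,000 WY. Independence is also doubtful: SAP 5.4.3 counts stopping for side effects as treatment failure, template Table C-1.3.1 lists depressive mood among those side effects, and Appendix III names current or worsening depression as a prognostic factor for treatment failure. The objection stands against the larger figures. The loss of about 5 points for anemia and for depression remains.

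Third, nothing in the plan makes success depend on all three hypotheses, so the joint figure is descriptive only.

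**Conclusion.** The point holds as an inconsistency in the decision rule. Both documents name Holm and describe Bonferroni, and the two can disagree on a primary hypothesis. Against Holm, the described rule gives up about 5 points of power each for anemia and depression (4 to 5 over assumed correlations of 0 to 0.8), almost nothing for treatment failure, and about 7 to 11 points for showing all three.

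A reader might infer that type I error is inflated. The described rule does not do that: one third of a common alpha for each test is valid. The exposure lies elsewhere, in the unadjusted 95% limits and, if its label is taken literally, in Table 4's one-sided 0.0167. A reader might also infer that the final analysis will in fact lose this power. The SAP does not support that either, because its 95% limits apply no correction at all.

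The figures rest on planned exposure and incidence. A footnote to SAP 3.1 reports that recruitment to the other-approved-medications cohort fell well short of plan. Realised power may therefore differ, but the documents give no exposure by cohort from which to recompute it.

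**What to change.** - Keep alpha/3 for sizing, and say that it is the first Holm step.
- In the SAP, state the step-down on one common sidedness: order the three one-sided p-values, test them at 0.00833, 0.0125 and 0.025, and stop at the first failure.
- Correct Table 4's alpha label to match Tables 2 and 3.
- In SAP 5.4.2.1 and the Section D tables, judge non-inferiority on the upper limit at the level of the Holm step reached (two-sided 98.33%, 97.5% or 95%) in place of the unadjusted 95% limit. Changing section 4 alone would leave the analysis uncorrected.

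The cost is wording and table templates only. No extra women or follow-up are needed, and familywise error stays at the intended level. One small downside is that limits read at the Holm step support the decision but lack simultaneous coverage; report Bonferroni-adjusted limits alongside if simultaneous intervals are wanted. Renaming the method Bonferroni would end the contradiction but keep the power loss, and the 95% limits and the Table 4 label would still need correcting.
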